8.1.3 ADVERSE EVENTS OF SPECIAL INTEREST (IMMEDIATELY REPORTABLE TO THE SPONSOR)

Adverse events of special interest are required to be reported by the Investigator to the Sponsor via the Covance Project Manager immediately (i.e., no more than 24 hours after learning of the event; see [Section 8.4.2](#) for reporting instructions). Adverse events of special interest for this study are as follows:

- Cases of potential drug-induced liver injury that include an elevated alanine aminotransferase (ALT) or aspartate aminotransferase (AST) in combination with either an elevated bilirubin or clinical jaundice, as defined by Hy’s Law (see [Section 8.3.1.6](#));
- Suspected transmission of an infectious agent by the study drug as defined below:
 - Any organism, virus, or infectious particle (e.g., prion protein transmitting transmissible spongiform encephalopathy), pathogenic or non-pathogenic, is considered an infectious agent. A transmission of an infectious agent may be suspected from clinical symptoms or laboratory findings that indicate an infection in a subject exposed to a medicinal product. The term applies only when a contamination of the study drug is suspected.
- All Grades syncope events;
- Grade ≥ 2 congestive cardiac failure;
- Grade ≥ 2 QT prolongation;

- Grade ≥ 3 cognitive disturbances (including confusion, mental status changes, hallucinations, or memory loss).

8.2 METHODS AND TIMING FOR CAPTURING AND ASSESSING SAFETY PARAMETERS

The Investigator is responsible for ensuring that all AEs (as defined in [Section 8.1](#)) are recorded on the AE eCRF and reported to the Sponsor via the Covance Project Manager in accordance with protocol instructions (see [Section 8.4.2](#)).

For each AE recorded on the AE eCRF, the Investigator will make an assessment of seriousness (see [Section 8.1.2](#) for seriousness criteria), severity, and causality (see [Sections 8.2.3](#) and [8.2.4](#)).

8.2.1 ADVERSE EVENT REPORTING PERIOD

Investigators will seek information on AEs at each subject contact. All AEs, whether reported by the subject or noted by study personnel, will be recorded in the subject's medical record and on the AE eCRF.

After informed consent has been obtained but prior to initiation of study drug administration, only SAEs caused by a protocol-mandated intervention (e.g., discontinuation of medications) will be reported (see [Section 8.4.2](#) for instructions for reporting SAEs). After initiation of study drug administration, all AEs will be reported until 28 days after the last dose.

Instructions for reporting AEs that occur after the AE reporting period are provided in [Section 8.5](#).

The Investigator is not required to actively monitor subjects after the study has ended or for AEs after the end of the AE reporting period (defined as 28 days after the last dose of study drug). However, the Sponsor should be notified if the Investigator becomes aware of any death, other SAEs, or AESIs occurring after the end of the AE reporting period that are believed to be related to prior study drug treatment. The Sponsor should also be notified if the Investigator becomes aware of the development of cancer or a congenital anomaly/birth defect in a subsequently conceived offspring of a female subject exposed to study drug (or the female partner of a male subject exposed to study drug).

8.2.2 ELICITING ADVERSE EVENT INFORMATION

A consistent methodology of non-directive questioning should be adopted for eliciting AE information at all subject evaluation timepoints. Examples of non-directive questions include the following:

- “How have you felt since your last clinic visit?”
- “Have you had any new or changed health problems since you were last here?”

8.2.3 ASSESSMENT OF SEVERITY OF ADVERSE EVENTS

The AE severity grading scale for the NCI CTCAE (version 5.0) will be used for assessing AE severity. Table 8-1 will be used for assessing AE severity for AEs that are not specifically listed in the NCI CTCAE.

Table 8-1 Adverse Event Severity Grading Scale for Events Not Specifically Listed in NCI CTCAE

Grade	Severity
1	Mild; asymptomatic or mild symptoms; clinical or diagnostic observations only; or intervention not indicated
2	Moderate; minimal, local, or non-invasive intervention indicated; or limiting age-appropriate instrumental activities of daily living ^a
3	Severe or medically significant, but not immediately life-threatening; hospitalization or prolongation of hospitalization indicated; disabling; or limiting self-care activities of daily living ^{b,c}
4	Life-threatening consequences or urgent intervention indicated ^d
5	Death related to adverse event ^d

NCI CTCAE = National Cancer Institute Common Terminology Criteria for Adverse Events.

Note: Based on the NCI CTCAE (v5.0), which can be found at:

http://ctep.cancer.gov/protocolDevelopment/electronic_applications/ctc.htm

^a Instrumental activities of daily living refer to preparing meals, shopping for groceries or clothes, using the telephone, managing money, etc.

^b Examples of self-care activities of daily living include bathing, dressing and undressing, feeding oneself, using the toilet, and taking medications, as performed by subjects who are not bedridden.

^c If an event is assessed as a “significant medical event,” it must be reported as an SAE (see [Section 8.4.2](#) for reporting instructions), per the definition of SAE in [Section 8.1.2](#).

^d Grade 4 and 5 events must be reported as SAEs (see [Section 8.4](#) for reporting instructions), per the definition of SAE in [Section 8.1.2](#).

8.2.4 ASSESSMENT OF CAUSALITY OF ADVERSE EVENTS

Investigators should use their knowledge of the subject, the circumstances surrounding the event, and an evaluation of any potential alternative causes to determine whether an AE is considered to

be related to the study drug, indicating “yes” or “no” accordingly. The following guidance should be taken into consideration (see also Table 8-2):

- Temporal relationship of event onset to the initiation of study drug;
- Course of the event, with special consideration of the effects of dose reduction, discontinuation of study drug, or reintroduction of study drug (as applicable);
- Known association of the event with the study drug or with similar treatments;
- Known association of the event with the disease under study;
- Presence of risk factors in the subject or use of concomitant medications known to increase the occurrence of the event;
- Presence of non-treatment-related factors that are known to be associated with the occurrence of the event.

Table 8-2 Causal Attribution Guidance

Is the adverse event suspected to be caused by the study drug based on facts, evidence, science-based rationales, and clinical judgment?	
YES	
There is a plausible temporal relationship between the onset of the adverse event and administration of the study drug, and the adverse event cannot be readily explained by the subject’s clinical state, intercurrent illness, or concomitant therapies; and/or the adverse event follows a known pattern of response to the study drug; and/or the adverse event abates or resolves upon discontinuation of the study drug or dose reduction and, if applicable, reappears upon re-challenge.
 
Investigators should apply facts, evidence, or rationales based on scientific principles and clinical judgment to support a causal/contributory association with a study drug.

NO	
Adverse events will be considered related, unless they fulfill the criteria as specified below.
 
Evidence exists that the adverse event has an etiology other than the study drug (e.g., pre-existing medical condition, underlying disease, intercurrent illness, or concomitant medication); and/or the adverse event has no plausible temporal relationship to administration of the study drug (e.g., cancer diagnosed 2 days after first dose of study drug).
 
Note: The Investigator’s assessment of causality for individual adverse event reports is part of the study documentation process. Regardless of the “Yes” or “No” causality assessment for individual adverse event reports, the Sponsor will promptly evaluate all reported serious adverse events against cumulative product experience to identify and expeditiously communicate possible new safety findings to Investigators and applicable regulatory authorities. Attribution of serious adverse events will be reviewed on an ongoing basis, and may be changed as additional clinical data emerges (e.g., reversibility of adverse event, new clinical findings in subject with adverse event, effects of re-treatment, and adverse events in other subjects).

8.3 PROCEDURES FOR RECORDING ADVERSE EVENTS

8.3.1 RECORDING ADVERSE EVENTS ON THE CASE REPORT FORM

Investigators should use correct medical terminology/concepts when recording AEs on the AE eCRF. Colloquialisms and abbreviations should be avoided.

All AEs should be recorded on the AE eCRF page. If the AE qualifies as an SAE or non-serious AESI, the Investigator should record all case details that can be gathered immediately (i.e., within 24 hours after learning of the event) on a paper Clinical Trial SAE/AESI Reporting Form. The completed paper Clinical Trial SAE/AESI Reporting Form and safety fax coversheet should be emailed to Roche Safety Risk Management via the Covance Project Manager within 24 hours of learning of the event (see [Section 8.4.2](#)). The AE and SAE eCRF should also be completed within this timeframe. It is important that the information on the SAE Reporting Form and AE and SAE eCRF is consistent and identical.

Only one AE term should be recorded in the event field on the AE eCRF.

8.3.1.1 DIAGNOSIS VERSUS SIGNS AND SYMPTOMS

If known, a diagnosis should be recorded on the AE eCRF rather than individual signs and symptoms (e.g., record only liver failure or hepatitis rather than jaundice, asterixis, and elevated transaminases). However, if a constellation of signs and/or symptoms cannot be medically characterized as a single diagnosis or syndrome at the time of reporting, each individual event should be recorded on the AE eCRF. If a diagnosis is subsequently established, all previously reported AEs based on signs and symptoms should be nullified and replaced by one AE report based on the single diagnosis, with a starting date that corresponds to the starting date of the first symptom of the eventual diagnosis.

8.3.1.2 ADVERSE EVENTS THAT ARE SECONDARY TO OTHER EVENTS

In general, AEs that are secondary to other events (e.g., cascade events or clinical sequelae) should be identified by their primary cause, with the exception of severe or serious secondary events. A medically significant secondary AE that is separated in time from the initiating event should be recorded as an independent event on the AE eCRF. For example:

- If vomiting results in mild dehydration with no additional treatment in a healthy adult, only vomiting should be reported on the eCRF;
- If vomiting results in severe dehydration, both events should be reported separately on the eCRF;
- If a severe gastrointestinal hemorrhage leads to renal failure, both events should be reported separately on the eCRF;
- If dizziness leads to a fall and subsequent fracture, all 3 events should be reported separately on the eCRF;
- If neutropenia is accompanied by an infection, both events should be reported separately on the eCRF.

All AEs should be recorded separately on the AE eCRF if it is unclear as to whether the events are associated.

8.3.1.3 PERSISTENT OR RECURRENT ADVERSE EVENTS

A persistent AE is one that extends continuously, without resolution between subject evaluation timepoints. Such events should only be recorded once in the AE eCRF. The initial severity (intensity or grade) of the event will be recorded at the time the event is first reported. If a persistent AE becomes more severe, the most extreme severity should also be recorded on the AE eCRF. If the event becomes serious, it should be reported to the Sponsor immediately (i.e., no more than 24 hours after learning that the event became serious; see [Section 8.4.2](#) for reporting instructions). The AE eCRF should be updated by changing the event from “non-serious” to “serious,” providing the date that the event became serious, and by completing all data fields related to SAEs.

A recurrent AE is one that resolves between subject evaluation timepoints and subsequently recurs. Each recurrence of an AE should be recorded as a separate event on the AE eCRF.

8.3.1.4 ABNORMAL LABORATORY VALUES

Not every laboratory abnormality qualifies as an AE. A laboratory test result should be reported as an AE if it meets any of the following criteria:

- Is accompanied by clinical symptoms;
- Results in a change in study treatment (e.g., dosage modification, treatment interruption, or treatment discontinuation);
- Results in a medical intervention (e.g., potassium supplementation for hypokalemia) or a change in concomitant therapy;
- Is clinically significant in the Investigator’s judgment.

It is the Investigator’s responsibility to review all laboratory findings. Medical and scientific judgment should be exercised in deciding whether an isolated laboratory abnormality should be classified as an AE.

If a clinically significant laboratory abnormality is a sign of a disease or syndrome (e.g., alkaline phosphatase and bilirubin 5 times the upper limit of normal (ULN) associated with cholestasis), only the diagnosis (i.e., cholestasis) should be recorded on the AE eCRF.

If a clinically significant laboratory abnormality is not a sign of a disease or syndrome, the abnormality itself should be recorded on the AE eCRF, along with a descriptor indicating whether the test result is above or below the normal range (e.g., “elevated potassium,” as opposed to “abnormal potassium”). If the laboratory abnormality can be characterized by a precise clinical term per standard definitions, the clinical term should be recorded as the AE. For example, an elevated serum potassium level of 7.0 mEq/L should be recorded as “hyperkalemia.”

Observations of the same clinically significant laboratory abnormality from visit to visit should only be recorded once on the AE eCRF (see [Section 8.3.1.3](#) for details on recording persistent AEs).

8.3.1.5 ABNORMAL VITAL SIGN VALUES

Not every vital sign abnormality qualifies as an AE. A vital sign result should be reported as an AE if it meets any of the following criteria:

- Is accompanied by clinical symptoms;
- Results in a change in study treatment (e.g., dosage modification, treatment interruption, or treatment discontinuation);
- Results in a medical intervention or a change in concomitant therapy;
- Is clinically significant in the Investigator’s judgment.

It is the Investigator’s responsibility to review all vital sign findings. Medical and scientific judgment should be exercised in deciding whether an isolated vital sign abnormality should be classified as an AE.

If a clinically significant vital sign abnormality is a sign of a disease or syndrome (e.g., high blood pressure), only the diagnosis (i.e., hypertension) should be recorded on the AE eCRF.

Observations of the same clinically significant vital sign abnormality from visit to visit should only be recorded once on the AE eCRF (see [Section 8.3.1.3](#) for details on recording persistent AEs).

8.3.1.6 ABNORMAL LIVER FUNCTION TESTS

The finding of an elevated ALT or AST ($>3 \times \text{ULN}$) in combination with either an elevated total bilirubin ($>2 \times \text{ULN}$) or clinical jaundice in the absence of cholestasis or other causes of hyperbilirubinemia is considered to be an indicator of severe liver injury (as defined by Hy’s Law). Therefore, Investigators must report the occurrence of either of the following as an AE:

- Treatment-emergent ALT or AST $>3 \times$ ULN in combination with total bilirubin $>2 \times$ ULN;
- Treatment-emergent ALT or AST $>3 \times$ ULN in combination with clinical jaundice.

The most appropriate diagnosis or (if a diagnosis cannot be established) the abnormal laboratory values should be recorded on the AE eCRF (see [Section 8.3.1](#)) and reported to the Sponsor immediately (i.e., no more than 24 hours after learning of the event), either as an SAE or an AESI (see [Section 8.4.2](#)).

8.3.1.7 DEATHS

All deaths that occur during the protocol-specified AE reporting period (see [Section 8.2.1](#)), regardless of relationship to study drug, will be recorded on the AE eCRF as well as on the paper Clinical Trial SAE Reporting Form and immediately reported to the Sponsor via the Covance Project Manager (see [Section 8.4.2](#) for reporting instructions).

Death should be considered an outcome and not a distinct event. The event or condition that caused or contributed to the fatal outcome should be recorded as the single medical concept on the AE eCRF. Generally, only 1 such event should be reported. If the cause of death is unknown and cannot be ascertained at the time of reporting, “unexplained death” should be recorded on the AE eCRF. If the cause of death later becomes available (e.g., after autopsy), “unexplained death” should be replaced by the established cause of death. The term “sudden death” should not be used unless combined with the presumed cause of death (e.g., “sudden cardiac death”).

Deaths that occur after the AE reporting period should be reported as described in [Section 8.5](#).

8.3.1.8 PRE-EXISTING MEDICAL CONDITIONS

A pre-existing medical condition is one that is present at the Screening visit for this study. Such conditions should be recorded on the General Medical History and Baseline Conditions eCRF page.

A pre-existing medical condition should be recorded as an AE only if the frequency, severity, or character of the condition worsens during the study. When recording such events on an AE eCRF, it is important to convey the concept that the pre-existing condition has changed by including applicable descriptors (e.g., “accelerated worsening of headaches”).

8.3.1.9 HOSPITALIZATION OR PROLONGED HOSPITALIZATION

Any AE that results in hospitalization (i.e., inpatient admission to a hospital) or prolonged hospitalization should be documented and reported as an SAE (per the definition of SAE in [Section 8.1.2](#)) except as outlined below.

An event that leads to hospitalization under the following circumstances should not be reported as an AE or SAE:

- Hospitalization for respite care;
- Hospitalization for a pre-existing condition, provided that all of the following criteria are met:
 - The hospitalization was planned prior to the study or was scheduled during the study when elective surgery became necessary because of the expected normal progression of the disease;
 - The subject has not experienced an AE.

An event that leads to hospitalization under the following circumstances is not considered to be an SAE but should be reported as an AE instead:

- Hospitalization that was necessary because of the subject's requirement for outpatient care outside of normal outpatient clinic operation hours.

8.4 IMMEDIATE REPORTING REQUIREMENTS FROM INVESTIGATOR TO SPONSOR

Certain events require immediate reporting to allow the Sponsor to take appropriate measures to address potential new risks in a clinical trial. The Investigator must report such events to the Sponsor immediately via the Covance Project Manager; under no circumstances should reporting take place more than 24 hours after the Investigator learns of the event. The following is a list of events that the Investigator must report to the Sponsor within 24 hours (see [Section 8.4.2](#)) after learning of the event, regardless of relationship to study drug:

- SAEs (see [Section 8.4.2](#) for further details);
- AESIs (see [Section 8.1.3](#) for further details);
- Pregnancies (see [Section 8.4.2.3](#) for further details);
- Accidental overdoses or medication errors (see [Section 8.4.3](#) for details on reporting requirements).

The Investigator must report new significant follow-up information for these events to the Sponsor immediately via the Covance Project Manager (i.e., no more than 24 hours after becoming aware of the information). New significant information includes the following:

- New signs or symptoms or a change in the diagnosis;
- Significant new diagnostic test results;
- Change in causality based on new information;
- Change in the event's outcome, including recovery;
- Additional narrative information on the clinical course of the event.

Investigators must also comply with local requirements for reporting SAEs to the local health authority and Institutional Review Board (IRB)/Ethics Committee (EC).

8.4.1 REPORTING REQUIREMENTS FOR FATAL OR LIFE-THREATENING SERIOUS ADVERSE EVENTS

Any life-threatening (e.g., imminent risk of death) or fatal AE that is attributed to study drug by the Investigator will be telephoned to the Medical Monitor immediately, followed by completion of the paper Clinical Trial SAE Reporting Form within 24 hours of learning of the event as described in Section 8.4.2.

Medical Monitor:

██████████

F. Hoffman-La Roche AG

██████████

(Office Telephone No.)

██████████

(Mobile Telephone No.)

8.4.2 REPORTING REQUIREMENTS FOR ALL SERIOUS ADVERSE EVENTS

8.4.2.1 EVENTS THAT OCCUR PRIOR TO STUDY DRUG INITIATION

After informed consent has been obtained but prior to initiation of study drug, only SAEs caused by protocol-mandated intervention should be reported. The paper Clinical Trial SAE/AESI Reporting Form provided to the Investigator should be completed and submitted to the Sponsor via the Covance Project Manager immediately (i.e., no more than 24 hours after learning of the event), either by faxing or by scanning and emailing the form using the fax number or email address provided below.

The Covance Project Manager to receive the Investigator-generated SAE reports:

Name: [REDACTED], RN, BSN, CCRC

Email Address: [REDACTED]

[REDACTED] (Office Telephone No.)

[REDACTED] (Mobile Telephone No.)

8.4.2.2 EVENTS THAT OCCUR AFTER STUDY DRUG INITIATION

After initiation of study drug, SAEs and AESIs will be reported until 28 days after the last dose of study drug. Investigators should record all case details that can be gathered immediately on a paper Clinical Trial SAE/AESI Reporting Form. The paper Clinical Trial SAE/AESI Reporting Form should be completed and submitted to the Sponsor (via the Covance Project Manager) immediately (i.e., no more than 24 hours after learning of the event), either by faxing or by scanning and emailing the form using the fax number or email address provided in [Section 8.4.2.1](#). All information will also need to be entered into the AE eCRF.

Relevant follow-up information should be submitted to Roche Safety Risk Management via the Covance Project Manager on an updated paper Clinical Trial SAE/AESI Reporting Form as soon as it becomes available and/or upon request. Any updates to the paper Clinical Trial SAE/AESI Reporting Form must also be updated in electronic data capture (EDC) on the AE eCRF.

8.4.2.3 REPORTING REQUIREMENTS FOR PREGNANCIES

8.4.2.3.1 PREGNANCIES IN FEMALE SUBJECTS

Female subjects of childbearing potential will be instructed to immediately inform the Investigator if they become pregnant during the study or within 28 days after the last dose of study drug. A paper Clinical Trial Pregnancy Reporting Form should be completed by the Investigator immediately (i.e., no more than 24 hours after learning of the pregnancy) and emailed to Roche Safety Risk Management via the Covance Project Manager (see [Section 8.4.2](#) for reporting instructions). Pregnancy should not be recorded on the AE eCRF. The Investigator should discontinue study drug and counsel the subject, discussing the risks of the pregnancy and the possible effects on the fetus. Monitoring of the subject should continue until conclusion of the pregnancy. Any SAEs associated with the pregnancy (e.g., an event in the fetus, an event in the mother during or after the pregnancy, or a congenital anomaly/birth defect in the child) should be reported on the AE eCRF. In addition, the Investigator will submit a paper Clinical Trial Pregnancy Reporting Form when updated information on the course and outcome of the pregnancy becomes available.

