5.3 INCLUSION CRITERIA

Subjects who meet the following criteria may be included in the study:

1. Males or females, between 18 and 60 years of age, inclusive, at Screening;
2. Within body mass index (BMI) range 18.0 to 32.0 kg/m², inclusive, and weighing at least 50 kg, at Screening;
3. Healthy in the opinion of the Investigator. Healthy is defined by the absence of evidence of any active disease or clinically significant medical condition based on a detailed medical history, physical examination, vital signs, 12-lead ECG, and laboratory safety test results;
4. Clinical laboratory evaluations (including chemistry panel [fasted at least 8 hours], complete blood count [CBC], and urinalysis [UA]) within the reference range for the test laboratory, unless deemed not clinically significant by the Investigator. Congenital nonhemolytic hyperbilirubinemia (eg, suspicion of Gilbert's syndrome based on total and direct bilirubin) is acceptable. In case of borderline or questionable results, tests may be repeated to confirm eligibility;

5. Negative test for selected drugs of abuse at Screening (does not include alcohol) and at Check-in (Day -1) of Period 1 (does include alcohol; [Appendix A](#));
6. Negative hepatitis panel (hepatitis B surface antigen and hepatitis C virus antibody) and negative HIV antibody screens ([Appendix A](#));
7. Females will not be pregnant or breastfeeding, and females of childbearing potential will agree to use highly-effective contraception as detailed in [Section 7.4](#);
8. Females of childbearing potential ([Section 7.4](#)) must agree to refrain from donating eggs during the treatment period and for 6 weeks after the final dose of study drug;
9. Males will agree to use contraception as detailed in [Section 7.4](#) and will refrain from sperm donation from Check-in (Day -1) of Period 1 and for 90 days after the final dose of study drug;
10. Able to comprehend and willing to sign an Informed Consent Form (ICF) and to comply with the study protocol and study restrictions.

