7.4 CONTRACEPTION

Postmenopausal is defined as at least 12 months without a period (i.e., amenorrhea) in a woman at least 45 years of age and documented by a serum follicle-stimulating hormone [FSH] level consistent with postmenopausal status (i.e., ≥ 40 IU/L) in the absence of a reversible medical iatrogenic cause. Surgically sterile is defined as permanently sterile via hysterectomy, bilateral oophorectomy, and/or bilateral salpingectomy by reported medical history and/or medical records for at least 90 days prior to Screening.

Females who are not postmenopausal or surgically sterile are of childbearing potential and must agree to use 1 of the following examples of highly-effective contraception (failure rate of $<1\%$ per year) from the time of signing the informed consent or 10 days prior to Check-in (Day -1) of Period 1 and for 6 weeks after the final dose of study drug:

- Bilateral tubal ligation;
- Bilateral tubal occlusion (Essure);
- Vasectomized male partner;
- Hormonal contraceptives that inhibit ovulation;
- Hormone-releasing intrauterine device (IUD);
- Copper IUD.

Male subjects will either be surgically sterile with documented azoospermia (confirmed by reported medical history and/or medical records) for at least 90 days prior to Screening, or will be required to use 1 of the following approved methods of contraception from Check-in (Day -1) of Period 1 and for 90 days after the final dose of study drug:

- Male condom with spermicide.

For subjects who are exclusively in same-sex relationships or are abstinent (when this is in line with the preferred and usual lifestyle of the subject), contraceptive requirements do not apply. If a subject who is in a same-sex relationship or abstinent at the time of signing the ICF becomes engaged in a heterosexual relationship, they must agree to use contraception as described previously.

Periodic abstinence (e.g., calendar, ovulation, symptothermal, post-ovulation methods) and withdrawal are not acceptable methods of contraception. If a male subject cannot provide proof of sterilization by medical records, the subject must agree to either true abstinence or a method of birth control as outlined above.

Male subjects (including men who have had vasectomies) whose partners are currently pregnant should use a barrier method with spermicide for the duration of the study through Follow-up. This is to ensure that the fetus is not exposed to the drug in the ejaculate.

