8.4.2.3.2 PREGNANCIES IN FEMALE PARTNERS OF MALE SUBJECTS

Male subjects will be instructed through the ICF to immediately inform the Investigator if their partner becomes pregnant during the study or within 28 days after the last dose of study drug. A paper Clinical Trial Pregnancy Reporting Form should be completed by the Investigator immediately (i.e., no more than 24 hours after learning of the pregnancy) and emailed to Roche Safety Risk Management via the Covance Project Manager (see [Section 8.4.2](#) for reporting instructions). Attempts should be made to collect and report details of the course and outcome of any pregnancy in the partner of a male subject exposed to study drug. When permitted by the site, the pregnant partner would need to sign an Authorization for Use and Disclosure of Pregnancy Health Information to allow for follow-up on her pregnancy. If the authorization has been signed, the Investigator should submit a Clinical Trial Pregnancy Reporting Form when updated information on the course and outcome of the pregnancy becomes available. An Investigator who is contacted by the male subject or his pregnant partner may provide information on the risks of the pregnancy and the possible effects on the fetus, to support an informed decision in cooperation with the treating physician and/or obstetrician.

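### The instruction to subjects to report a pregnancy (during the study or 28 days after the last dose) covers less time than the protocol's own precautions against conception (6 weeks for women, 90 days for men), and no reason is given

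*Protocol*

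**What the plan says.** **Instruction to subjects.** Protocol 8.4.2.3.1 has women of childbearing potential inform the Investigator "if they become pregnant during the study or within 28 days after the last dose of study drug". Section 8.4.2.3.2 has men do so "if their partner becomes pregnant during the study or within 28 days after the last dose of study drug", and says that men receive this instruction through the consent form.

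**Precautions.** Section 7.4 requires women of childbearing potential to use highly effective contraception "for 6 weeks after the final dose of study drug", and non-sterile men to use contraception "for 90 days after the final dose of study drug". Section 5.3 sets matching limits on gamete donation: women "must agree to refrain from donating eggs during the treatment period and for 6 weeks after the final dose of study drug", and men "will refrain from sperm donation from Check-in (Day -1) of Period 1 and for 90 days after the final dose of study drug".

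**Duties on the Investigator.** Section 8.4 introduces its list with "The following is a list of events that the Investigator must report to the Sponsor within 24 hours", and pregnancies are on that list. Section 8.4.2.3.3 makes birth defects and abortions reportable. Section 8.2.1 asks that the Sponsor be told of a birth defect in offspring conceived later, if the Investigator hears of it. Section 8.5 has subjects told at the end of follow-up to report later adverse events that their own physician thinks could be related.

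**The concern.** The protocol treats fetal exposure as a risk to be managed. Section 2.1.2 reports developmental abnormalities in rats (at doses that were also toxic to the mother), and Section 2.4 names contraception as one of the mitigations. Sections 5.3 and 7.4 then define a period after dosing in which conception is to be avoided. One would expect subjects to be asked to report any conception in that period. The instruction covers only its first part, so a contraceptive failure late in the period is one that subjects are not asked to mention.

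After the telephone call 12 to 14 days after the last dose, no contact is scheduled. Table 7-1 makes Follow-up a telephone call, so no scheduled serum pregnancy test comes after discharge from Period 2. From then on the site learns of a pregnancy only if someone volunteers it, which is why the wording of the instruction matters. What is at stake is the completeness of pregnancy safety reporting. The pharmacokinetic comparison and the sample size are not affected.

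**Working it through.** The plan gives no figure of its own to reproduce. The check is a comparison of windows in days after the last dose.

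**Inputs**
- Reporting window after the last dose: 28 days (8.4.2.3.1, 8.4.2.3.2).
- Precaution window, women: 6 weeks = 6 × 7 = 42 days (5.3, 7.4).
- Precaution window, men: 90 days (5.3, 7.4).
- Last scheduled contact: 12 to 14 days after the last dose (Synopsis, 4.1).
- End of study: when the final subject has had their final planned procedure (4.1).
- Half-lives: entrectinib about 20 to 30 h, M5 about 40 h (4.2).

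**Step 1. Size of the gap: precaution window minus reporting window**
- Women: 42 − 28 = 14 days (days 29 to 42).
- Partners of men: 90 − 28 = 62 days (days 29 to 90).

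**Step 2. Does the reference to the study period close it?** Take a subject whose last dose comes *d* days before the last subject's. The study then ends no later than about that subject's post-dose day *d* + 14.
- If *d* is 14 or less, that is day 28 or earlier, and the study period adds nothing to the 28 days.
- If *d* is more than 14, the study period runs past day 28 and the gap shrinks. It would close for women at *d* = 42 − 14 = 28, and for men only at *d* = 90 − 14 = 76.

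So 14 and 62 days are maxima. They apply in full to anyone dosed within 14 days of the last subject.

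**Step 3. Is there a stated reason?** The 28 days matches the period for adverse event reporting in 8.2.1 and for SAE and AESI reporting in 8.4.2.2, but no section offers this as the reason for the pregnancy window. Elimination is another candidate: 28 × 24 = 672 h, which is 672/40 = 16.8 M5 half-lives and 672/30 = 22.4 to 672/20 = 33.6 entrectinib half-lives. The protocol does not give that reason either. With the same half-lives it sets precautions that last 42 × 24/40 = 25.2 and 90 × 24/40 = 54 M5 half-lives.

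**Step 4. How many events?** Section 7.4 puts the failure rate of the women's methods below 1% per year. Assume the extreme case that all 14 subjects are women of childbearing potential, that all use such a method, and that risk is constant over time. Expected conceptions on days 29 to 42 are then below 14 × (14/365) × 0.01 = 0.0054. Section 7.4 gives no failure rate for the male method, so no figure is offered for partners.

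**The case against.** The strongest reply is that the windows do different jobs. Contraception prevents exposure, with a margin; reporting captures pregnancies around exposure. By day 28 almost no drug remains: with first-order elimination, 16.8 half-lives leave about 0.001% of M5. The 28 days is also the period used for safety reporting throughout Section 8. On this view a precaution window longer than the reporting window is not incoherent. That much stands, and it is why the point is a mismatch and not an error. But the protocol does not give this reasoning, and it keeps precautions in force well past day 28 with the same half-lives in view.

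A second reply is that Section 8.5 is a standing instruction to subjects with no end date. That narrows the gap: a birth defect or abortion thought related to study drug could reach the site this way. It does not clearly cover an uncomplicated pregnancy. It concerns adverse events that a physician believes could be related, and 8.4.2.3.1 keeps pregnancy itself off the adverse event form.

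A third reply is that the lack of contact after the telephone call applies equally to days 15 to 28. That is correct, and a longer instruction would leave follow-up passive. The difference is that until day 28 the subject has been asked to report, and afterwards has not.

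Finally, the consent form is not among the documents reviewed, so what men are actually told cannot be seen. The point concerns the protocol text only.

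**Conclusion.** The point holds as a minor one. Once the study has ended, up to 14 post-dose days for women and up to 62 for partners lie inside the protocol's own precaution period but outside the instruction to subjects, and no reason is stated.

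Two stronger readings are tempting and are not supported. A reader might infer that the sections contradict each other. They do not: a subject can follow the precautions and the reporting instruction together. A reader might also infer that a pregnancy beginning after day 28 need not be reported at all. Section 8.4 says otherwise. The Investigator must report a pregnancy once aware of it, and the reporting-form requirements in 8.4.2.3.1 and 8.4.2.3.2 run from learning of it, with no cut-off of their own. The gap lies only in what subjects are asked to volunteer.

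The day counts rest on the windows as written and are upper limits, because subjects dosed early remain in the study period for longer. They measure calendar time, not missed events. The only event figure available, for women, is very small.

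**What to change.** Reconcile the window in 8.4.2.3.1 and 8.4.2.3.2, and the matching consent-form instruction, with the precaution windows in 5.3 and 7.4, so that subjects are asked about pregnancies throughout whatever precaution period the protocol sets. The durations themselves are for the sponsor's clinical team, and this review takes no view on which is right. Adding a rationale for the present difference would document it but would not close the gap.

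The cost is protocol and consent-form wording, and possibly a few more weeks of passive pregnancy reporting. No extra visit, sample or analysis is needed.
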